Visit 1 (Week 0, Day 1, start of treatment)

- Measurement of the body weight;
- Collection of complaints and anamnesis;
- Registration of concomitant therapy;

- Assessment of the main vital signs (BP, HR, RR, body temperature);
- Physical examination of joints;
- Evaluation of inclusion/non-inclusion criteria;
- Injection of the studies MD into the cavity of the target joint (only for group A patients who are shown to receive the injection in accordance with the criteria specified in the Protocol);
- Registration of AE and SAE;
- Evaluation of exclusion criteria.

Every 2 weeks between Visit 1 and Visit 3 (weeks 3, 5, 7, 9 and 11), telephone contacts are made with the patient to clarify complaints, AE and the need for taking paracetamol or NSAIDs for the past 2 weeks. If AE is detected, or the need to take paracetamol or NSAIDs more than 4 days a week in each of the consecutive 2 weeks, the patient is invited to the clinic for an unscheduled Visit or a Visit to prematurely complete participation in the study (depending on the reason for the visit).

Visit 2 (Week 1, Day 8, treatment and follow-up) - as indicated

Only patients who received an injection of MD NOLTREXTM into the target knee joint on Visit 1 are eligible for Visit 2.

The following procedures must be performed during the visit:

- Measurement of the body weight;
- Collection of complaints and anamnesis;
- Registration of concomitant therapy;
- Assessment of the main vital signs (BP, HR, RR, body temperature);
- Physical examination of joints;
- Assessment of the severity of pain in the target knee joint using 100-mm VAS;
- Injection of the studied MD into the target joint cavity (only for patients of group A, in which the severity of pain in the target knee joint using 100 mm VAS did not decrease by 40% or more compared to the assessment on the Visit 0);
- Evaluation of the patient's diary;
- Return of the diary to the patient;
- Registration of AE and SAE;
- Evaluation of exclusion criteria.

Visit 3 (Week 13, Day 84 ± 2, treatment and follow-up)

- Measurement of the body weight;
- Collection of complaints and anamnesis;
- Registration of concomitant therapy;
- Assessment of the main vital signs (BP, HR, RR, body temperature);
- Physical examination of joints;
- Filling out algofunctional questionnaire WOMAC with an assessment of the subscales of pain (WOMAC-A), stiffness (WOMAC-B) and functional performance (WOMAC-C);

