- d. Serious deviation from the research Protocol;
- e. Erroneous inclusion (for example, the patient was included in violation of the Protocol's inclusion/non-inclusion criteria);
- f. The patient receives/needs additional treatment that may affect the outcome of the study or the patient's safety (for more information, see the section "Prohibited concomitant therapy");
- g. Injury to the target knee joint;
- h. Other conditions or events that, in the opinion of the research doctor, require the patient to be excluded from the study.

If patients included in the study are found to have reasons for completing the study prematurely, they are excluded from the study at the stage of identifying these reasons. Each case of premature completion of the study by the patient or withdrawal of the patient from the study must be documented with the mandatory indication of the reason for premature completion/withdrawal from the study, as well as reporting to the Sponsor within 7 business days.

Prohibited concomitant therapy

- 1. Glucocorticosteroids in any dosage form;
- 2. Any intra-articular and periarticular injections;

3. Use of NSAIDs and painkillers that are not approved by the Protocol, including local ones (with the exception of paracetamol and NSAIDs allowed by the Protocol in case of ineffectiveness of paracetamol);

4. Use of paracetamol at a dose of more than 4000 mg per day;

5. Use of one of the Protocol-approved NSAIDs in doses exceeding the permitted doses (permitted drugs and doses: diclofenac potassium 50 mg 2 times a day, diclofenac sodium tablets 75 mg 2 times a day, naproxen tablets 500 mg 2 times a day, naproxen sodium tablets 550 mg 2 times a day, meloxicam tablets 7.5 mg once a day, celecoxib tablets 200 mg 2 times a day);

6. Use of a combination of paracetamol with NSAIDs or a combination of two or more NSAIDs;

7. Surgical interventions and arthroscopies on the target knee joint.

Justification of the sample size

This open-label MD NOLTREXTM safety assessment study includes eligible and non-eligible patients who received MD NOLTREXTM as part of the IA/PAAG-SI/OA/2019 study. Therefore, no formal calculation of the sample size was performed. The maximum expected number of study participants is the number of patients who were randomized to the MD NOLTREXTM group in the IA/PAAG-SI/OA/2019 study, i.e. 72 patients.

Blinding, randomization

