#### **3.1.3.** Analysis of efficacy parameters

Main efficacy parameters of the studied MD:

1. Change in the overall score on the WOMAC scale (WOMAC-T) on Visit 3 (week 13), Visit 5 (week 25) compared to the basal value on Visit 0 (screening) of the open study and compared to the basal value on Visit 1 (week 1) of the IA/PAAG-SI/OA/2019 study;

2. Change in the pain subscale score (WOMAC-A) on Visit 3 (week 13), Visit 5 (week 25) compared to the basal value on Visit 0 (screening) of the open study and compared to the basal value on Visit 1 (week 1) of the IA/PAAG-SI/OA/2019 study;

3. Change in the score for stiffness subscale (WOMAC-B) and functional performance (WOMAC-C) at Visit 3 (week 13), Visit 5 (week 25) compared to the basal value at Visit 0 (screening) of open study and compared to the basal value at Visit 1 (week 1) of the study IA/PAAG-SI/OA/2019;

4. The change in the severity of pain in the target knee on a 100-mm VAS at Visit 2 (week 1), Visit 3 (week 13), Visit 5 (week 25) compared to the basal value at Visit 0 (screening) of open safety study and compared to the basal value at Visit 1 (week 1) study IA/PAAG-SI/OA/2019;

5. Evaluation of the effectiveness of treatment by the patient, parameter OEP (on a scale from 1-clear deterioration to 6-significant improvement) on Visits 3 and 5 (parameters OEP-w13 and OEP-w25, respectively);

6. Evaluation of the effectiveness of treatment by the investigator, parameter OEI (on a scale from 1-clear deterioration to 6-significant improvement) on Visits 3 and 5 (parameters OEI-w13, OEI-w25, respectively);

7. Assessment of the total number of paracetamol tablets taken (one tablet = 500 mg) starting from day 1 on Visits 3 and 5 (PARACETAMOL -w13 and PARACETAMOL-w25, respectively);

8. Assessment of the total number of NSAID tablets taken starting from day 1 on Visits 3 and 5 (NSAID-w13 and NSAID-w25, respectively);

9. The parameter JSN of the target knee joint at Visit 5 of the open study compared to the basal value on Visit 0 of the IA/PAAG-SI/OA/2019 study retrospectively.

All performance parameters will be analyzed both among all patients included in open study no. IA/PAAG-SI/OA/2020 (using descriptive statistics) and in subgroups of patients:

- those who received only one course of injections in the placebo-controlled study IA/PAAG-SI/OA/2019;
- those who received two courses of therapy both in the placebo-controlled and at Visit 1 (and as per the indications at Visit 2) of the open study;

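### Frequent use of allowed analgesics may end a patient's participation, but no rule says when, so follow-up can stop because of high values of an efficacy outcome

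*Protocol*

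**What the plan says.** **Telephone contacts (Protocol, Patient visits, under Visit 1 and Visit 3).** Calls are listed for weeks 3 to 11 and 15 to 23. There are two triggers: an AE, or "the need to take paracetamol or NSAIDs more than 4 days a week in each of the consecutive 2 weeks". If either is met, "the patient is invited to the clinic for an unscheduled Visit or a Visit to prematurely complete participation in the study". The choice between the two visits is made "depending on the reason for the visit", and nothing further is said about it.

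**Prohibited concomitant therapy (Protocol).** Item 3 bans unapproved analgesics, "with the exception of paracetamol and NSAIDs allowed by the Protocol in case of ineffectiveness of paracetamol". Items 4 to 6 then ban "Use of paracetamol at a dose of more than 4000 mg per day"; "Use of one of the Protocol-approved NSAIDs in doses exceeding the permitted doses"; and "Use of a combination of paracetamol with NSAIDs or a combination of two or more NSAIDs". None limits days of use.

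**Exclusion criteria (Protocol).** None of a to h mentions how often analgesics are taken. Criteria b and h rest on the investigator's judgement. Criterion f covers additional treatment that may affect the outcome and points to the prohibited list.

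**Outcomes.** SAP 3.1.3, item 7, is "Assessment of the total number of paracetamol tablets taken (one tablet = 500 mg) starting from day 1", evaluated at Visits 3 and 5. Item 8 is the same count for NSAIDs.

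**Missing data (SAP 3.6).** No data recovery is provided for any efficacy, safety or tolerability parameter. Missing values are said not to be missing at random, but the reason given is that subgroups follow treatment need. The telephone rule is not mentioned.

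**The concern.** The quantity that can end follow-up is also the quantity being measured. The need for paracetamol and NSAIDs is part of the second study task, and tablet totals are two of the nine efficacy parameters. If a site ends participation when use is frequent, the heaviest users leave before Visit 3 or Visit 5 and the totals at those visits come from lighter users.

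The loss goes beyond tablet counts. Scheduled WOMAC and VAS at Visits 3 and 5 are missing for the same patients. Knee radiography is scheduled at Visit 5 but is not among the premature-completion procedures, so joint space narrowing is lost. AE follow-up ends early in a study whose main purpose is safety. A Group B patient stopped at weeks 3 to 11 never reaches the re-injection assessment at Visit 3 and so stays in the one-course subgroup.

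With four centres and no rule linking reason to visit, sites may act differently.

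**Working it through.** The plan has no figure of its own to reproduce: 72 is a ceiling and no sample size was calculated.

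**1. Can the trigger be met within the permitted limits?** More than 4 days a week means at least 5, so the trigger is at least 5 × 2 = 10 analgesic days in 14. The paracetamol limit is 4000/500 = 8 tablets a day. One tablet on 5 days a week for 2 weeks is 10 tablets, against a permitted 8 × 14 = 112. So yes, with paracetamol alone and no combination.

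**2. How much follow-up is lost?** Day 1 to Day 169 is 168 days. Observed share = contact week × 7/168.
- Week 3: 21/168 = 12.5%
- Week 11: 77/168 = 46%
- Week 23: 161/168 = 96%

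**3. Effect on tablet totals.** The documents give no usage rates, so these are assumptions: 24 weeks; 2 tablets per day of use; each patient's daily probability of use drawn from a beta distribution; a patient is stopped at a listed call if both preceding weeks had more than 4 days of use. With s the share meeting the trigger, F the mean total if everyone were followed and C the mean in completers when every trigger ends participation, the understatement is 1 − C/F. If only a fraction q of triggered patients is stopped, the completer mean is

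C(q) = [F − q(F − (1 − s)C)] / (1 − qs).

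| Distribution (mean days/week) | s | F | C | 1 − C/F | C(0.5) | 1 − C(0.5)/F |
|---|---|---|---|---|---|---|
| Beta(1,4) (1.4) | 7% | 67 | 58 | 13.4% | 62.7 | 6.5% |
| Beta(1,3) (1.8) | 13% | 84 | 66 | 21.4% | 75.6 | 10.0% |
| Beta(1,2) (2.3) | 24% | 112 | 76 | 32.1% | 96.5 | 13.9% |
| Beta(2,3) (2.8) | 31% | 135 | 101 | 25.2% | 121.1 | 10.3% |

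Worked for the third row at q = 0.5: F − (1 − s)C = 112 − 0.76 × 76 = 54.24; (112 − 27.12)/(1 − 0.12) = 96.5; 1 − 96.5/112 = 13.9%. The inputs are rounded and simulated, so the upper end of the half case is 13% to 14%. At q = 0 the bias is nil.

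**4. Counting the truncated totals instead of dropping them.** When every trigger ends participation, using the shortened totals as if complete still understates the mean by 12% to 34%. A hand check gives the same direction. Take 20% of patients at 240 tablets and 80% at 48, a mean of 0.2 × 240 + 0.8 × 48 = 86.4. If the heavy users stop at week 11 they have 240 × 77/168 = 110 recorded, and the mean becomes 0.2 × 110 + 0.8 × 48 = 60.4, which is 70% of the full value.

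No pain score was simulated.

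**The case against.** A reader might infer a flat contradiction: that the telephone rule removes frequent users while the other rules permit them to stay. The documents do not support that. The unscheduled visit is an equal alternative, and analgesic need is assigned to neither visit. The exclusion criteria are silent on frequency, which is not permission, and b, f and h leave room to withdraw such a patient. There is also a consistent reading. The unscheduled visit includes a check of the exclusion criteria, and patients are excluded once a reason is identified, so the call may simply prompt that check.

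A reader might also infer that analgesic need and pain will be understated by up to a third. That needs every trigger to end participation and the assumed usage to be right; for WOMAC and VAS the effect is inference only.

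It also counts against the concern that the premature-completion visit records WOMAC, VAS, both global ratings, laboratory tests, AEs and both tablet totals. SAP 3.6 already concedes non-random missingness and promises that missing data will be reported. Safety is the main purpose, and the whole-cohort efficacy analysis is descriptive.

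All of this stands, and it limits the point. It does not remove it. Discretion leaves outcome-dependent stopping to each site, exit values are not Visit 3 or Visit 5 values, and no rule says whether a truncated total counts as the week 13 or week 25 total.

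**Conclusion.** The point holds as an unreconciled gap. The protocol allows frequent use of allowed analgesics to lead to premature completion, does not say when, and has no exclusion or concomitant-therapy rule that names frequency. Where that option is used, follow-up is cut short by the value of an efficacy outcome, and the SAP has no handling for it.

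The direction is clear: tablet totals are understated whenever the trigger ends participation. The size is not known. Under the assumed usage it is about 13% to 32% if every trigger ends participation, about 6% to 14% if half do, and nil if none do. Closing the gap is a cheap improvement to the efficacy results and to the completeness of safety follow-up.

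**What to change.** 1. **Protocol.** Reconcile the telephone-contact text under Visits 1 and 3 with the Exclusion criteria and Prohibited concomitant therapy, and state which reason leads to which visit. No view is taken here on which clinical rule is right.
2. **Data collection.** Whatever the clinical decision, keep collecting the already scheduled WOMAC, VAS, diary, radiography and AE data to Visit 5 in patients who still consent. Record the reason for each premature-completion visit so that analgesic frequency can be told apart from an AE or another cause.
3. **SAP 3.1.3 and 3.6.** State that truncated tablet totals are not used as week 13 or week 25 totals but are analysed as tablets per observed day. Add a sensitivity analysis for patients stopped after the trigger. It is needed because a rate that ends on a heavy fortnight may not represent the unobserved weeks.

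The cost is a wording amendment, one reason field, and a few patients attending visits already on the schedule. Analgesic totals may look less favourable.

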## List of abbreviations

Abbreviation	Meaning
BP	Blood pressure
ALT	Alanine aminotransferase
anti-HCV	Total antibodies to Hepatitis C Virus
AST	Aspartate aminotransferase
ATC	Anatomical-therapeutic-chemical classification
APTT	Activated partial thromboplastin time
VAS	Visual-analog scale
HIV	Human immunodeficiency virus
GGTP	Gamma-glutamyl transpeptidase
DEE	Confidence interval
CS	Clinical study
CRO	Contract research organization
MD	Medical device
GCP	Good clinical practice
NSAIDs	Non-steroidal anti-inflammatory drugs
IEC	Independent ethics committee
AE	Adverse event
OA	Osteoarthrosis
РТ	Prothrombin time
SAE	Serious adverse event
SOP	Standard operating procedure
ESR	Erythrocyte sedimentation rate
CRD	Chronic renal disease
RR	Respiration rate
HR	Heart rate
ALP	Alkaline phosphatase
eCRF	electronic Case Report Form
ACR	American College of Rheumatology
HBs-Ag	hepatitis B surface antigen

ІСН	International council for harmonization of technical requirements for pharmaceuticals for human use
JSN	Joint space narrowing
JSW	Joint space width
MedDRA	Medical Dictionary for Regulatory Activities
OEI	Evaluation of the treatment effectiveness by the investigator
OEP	Evaluation of the treatment effectiveness by the patient
WOMAC	Western Ontario and McMaster Universities Osteoarthritis
WOMAC-A	Subscale of pain according to the osteoarthritis index developed by researchers at the Western Ontario and McMaster Universities Osteoarthritis
WOMAC-B	Subscale of stiffness according to the osteoarthritis index developed by researchers at the Western Ontario and McMaster Universities Osteoarthritis
WOMAC-C	Subscale of function according to the osteoarthritis index developed by researchers at the Western Ontario and McMaster Universities Osteoarthritis
WOMAC-T	Change in the total score on the scale of the osteoarthritis index, developed by the researchers at the Western Ontario and McMaster Universities Osteoarthritis

## 1.1 General provision

#### 1.1.1 Justification of selection of the clinical study type

An open-label intervention study in one group with OA patients who received a single course of injections of the NOLTREXTM medical device as part of the IA/PAAG-SI/OA/2019 study.

The open nature of the study in one group is determined by the main purpose of the study - to assess the safety of MD NOLTREXTM with a single or repeated course of use. It is assumed that continued monitoring of patients in the placebo group will not lead to the identification of new AEs, the frequency of which should be compared with the frequency in the active therapy group, and is connected to unethical restriction of patients in the placebo group from the possibility to use potentially effective synovial fluid endoprostheses.

#### 1.1.1.1 Graphical diagram of the study

### 1.1.2 Measures aimed to minimize subjectivity

The open nature of the study in one group is determined by the main purpose of the study - to assess the safety of MD NOLTREXTM with a single or repeated course of use. Placebo safety data at the 6month point (Visit 5) in the IA/PAAG-SI/OA/2019 study will be used as a control. It is assumed that continued monitoring of patients in the placebo group will not lead to the identification of new AEs, the frequency of which should be compared with the frequency in the active therapy group, and is connected to unethical restriction of patients in the placebo group from the possibility to use potentially effective synovial fluid endoprostheses.

At the same time, many of the recorded performance parameters are objective (an assessment of the total number of paracetamol tablets or other NSAIDs taken from the patient's diary) or do not depend on the subjectivity of the investigator's assessment (parameters of evaluation on the scales WOMAC, VAS, OEP). The measurement of the JSW parameter is objective with strict adherence to the measurement methodology.

When evaluating the safety parameters, objective data is also recorded (for subjective assessment of the patient's tolerability of therapy, which does not depend on the subjectivity of the investigator's

assessment). Overall assessment of the treatment tolerability by the research physician will also be based on a comparison of objective data with basal parameters, which also minimizes subjectivity.

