gonarthrosis (IA/PAAG-SI/OA/2019) was conducted, in which 72 patients aged over 50 years with a verified diagnosis of gonarthrosis in accordance with the criteria of the American College of Rheumatology (ACR) II-III radiological stage classification Kellgren-Lawrence received 1 to 2 injections (at 1-week intervals) of 4 mL of MD NOLTREXTM into the most affected (target) knee joint. The second injection was not performed if the severity of pain in the target knee joint decreased by 40— or more a week after the first injection. The study was performed to evaluate the effectiveness and safety of MD NOLTREXTM with this method of use in comparison with placebo.

The current study is planned to include patients who received at least one intra-articular injection of MY NOLTREX[™] in IA/PAAG-SI/OA/2019 study and underwent procedures during the 5-week Visit (25 weeks – 6 months after the injection). After completing all the procedures of Visit 5 and completing the corresponding electronic individual registration card (eCRF) forms in the IA/PAAG-SI/OA/2019 study, the investigator receives information about which group in the IA/PAAG-SI/OA/2019 study the patient was assigned to, i.e. whether he received injections of the study MD or placebo. After that, patients who received the studied MD will be asked to sign an informed consent form to participate in the open clinical trial IA/PAAG-SI/OA/2020.

Procedures of Visit 5 (25 weeks - 6 months after injection) of the placebo-controlled trial IA/PAAG-SI/OA/2019, if they coincide with the screening procedures of Visit 0 of the open trial IA/PAAG-SI/OA/2020 for patients who have agreed to participate in this study and are eligible to participate, will be considered as procedures Visit 0 of the open trial IA/PAAG-SI/OA/2020. Thus, Visit 5 of the IA/PAAG-SI/OA/2019 study coincides with the screening Visit (Visit 0) of the IA/PAAG-SI/OA/2020 study.

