- Physical examination of joints;
- Assessment of the severity of pain in the target knee joint using 100-mm VAS;
- Injection of the studied MD into the target joint cavity (only for patients of Group B, in which the severity of pain in the target knee joint using 100 mm VAS did not decrease by 40% or more compared to the assessment at Visit 3)
- Evaluation of the patient's diary;
- Return of the diary to the patient;
- Registration of AE and SAE;
- Evaluation of exclusion criteria.

Visit 5 (Week 25, Day 169 ± 2 , follow-up)

- Measurement of the body weight;
- Collection of complaints and anamnesis;
- Registration of concomitant therapy;
- Assessment of the main vital signs (BP, HR, RR, body temperature);
- Physical examination of joints;
- Radiography of the knee joints and documentation of parameters of joint space width (JSW) and joint space narrowing (JSN);
- Filling out algofunctional questionnaire WOMAC with an assessment of the subscales of pain (WOMAC-A), stiffness (WOMAC-B) and functional performance (WOMAC-C);

- Assessment of the severity of pain in the target knee joint using 100-mm VAS;
- Evaluation of the effectiveness of treatment by the patient, OEP parameter;
- Evaluation of the effectiveness of treatment by the investigator, OEI parameter;
- Clinical blood test (hemoglobin level, hematocrit, red blood cell count, white blood cell formula, platelet count, ESR);
- Biochemical blood test (glucose, ALT, AST, ALP, GGTP, total bilirubin, creatinine, uric acid, rheumatoid factor);
- Coagulogram (APTT, PT, prothrombin index, fibrinogen);
- General urinalysis (color, transparency, relative density, pH, glucose, protein, ketone bodies, urobilinogen);
- Evaluation of the patient's diary;
- Evaluation of the total number of paracetamol tablets taken (one tablet = 500 mg) using patient's diary, PARACETAMOL parameter;
- As per patient's diary, evaluation of the total number of NSAIDs allowed by the Protocol in case of paracetamol inefficiency (NSAIDs allowed by the Protocol in case of paracetamol inefficiency: diclofenac potassium tablets 50 mg, diclofenac sodium tablets 75 mg, naproxen tablets 500 mg, naproxen sodium tablets 550 mg, meloxicam tablets 7.5 mg, celecoxib tablets 200 mg), NSAID parameter;
- Registration of AE and SAE;
- Evaluation of exclusion criteria.

An unscheduled visit

The following procedures must be performed during the visit:

- Measurement of the body weight
- Collection of complaints and anamnesis;

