This study is planned as an open-label study in a single group with subsequent division into subgroups depending on the actual need for treatment. In this regard, the Protocol does not provide for blinding and randomization.

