## **3.6.** Procedures to count the missing, non-analyzable, and questionable data

During the monitoring visits to the clinical center, the monitoring specialists authorized by the sponsor will conduct an analysis of patient's eCRF to identify any lack of necessary data. In the absence of data in the eCRF and the availability of relevant information in the primary documentation, the questions to the investigators and instructions for eliminating the inconsistencies will be formulated.

The statistician, authorized by the sponsor, and the principal investigator, when checking the database of research results, will analyze for the presence of dubious, missing and non-analyzable data, and will also formulate questions for investigators.

Researchers, if possible, will eliminate the identified errors in eCRF and inform the main researcher and authorized representatives of the sponsor about this. If the detected errors in the data cannot be eliminated after the completion of patient participation in the study, the statistical analysis of the data will be used to analyze the sensitivity of the resulting parameters to the doubtful data found. Information about the missing, doubtful and non-analyzable data will be presented in the final clinical trial report.

For all parameters of efficacy, safety and tolerability, data recovery is not provided due to the fact that the distribution of patients into subgroups for analysis is based on the actual need for treatment, and is not based on any procedures for distribution into groups, so the missing values cannot be considered as missing accidentally or completely accidentally.

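### SAP 1.1.2 relies on joint-space width being objective, but the supplied documents do not mask the film reader to the open re-injection that defines the subgroups in which JSN is tested

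*SAP*

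**What the plan says.** - **Claimed safeguard.** SAP 1.1.2 (Measures aimed to minimize subjectivity) lists reasons why the open design should not bias the results. On the radiographic measure it says "The measurement of the JSW parameter is objective with strict adherence to the measurement methodology". The supplied text does not describe that methodology.
- **Blinding.** The protocol's section on blinding and randomization says "In this regard, the Protocol does not provide for blinding and randomization". It makes no separate provision for image reading.
- **Knowledge of treatment.** Before entry "the investigator receives information about which group in the IA/PAAG-SI/OA/2019 study the patient was assigned to", and only patients who had the device in 2019 are eligible. Re-injection at Visits 1-2 (Group A) or Visits 3-4 (Group B) is given openly.
- **Measurement.** Protocol Visit 5 lists "Radiography of the knee joints and documentation of parameters of joint space width (JSW) and joint space narrowing (JSN") as a procedure. No reader, reading site or reading order is named. The Visit 0 procedures of the open study list no radiograph.
- **Endpoint.** Item 9 of SAP 3.1.3 is JSN of the target knee at Visit 5, "compared to the basal value on Visit 0 of the IA/PAAG-SI/OA/2019 study retrospectively".
- **Analysis.** SAP 3.1.3 summarises all efficacy parameters descriptively in all patients. It also compares them across three subgroups: no re-injection, re-injection from Visit 1, and re-injection from Visit 3. Quantitative parameters not based on WOMAC get analysis of variance, and qualitative ones get chi-square. SAP 3.4 sets a two-sided 5% level.
- **How subgroups arise.** SAP 3.6 says "the distribution of patients into subgroups for analysis is based on the actual need for treatment".

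**The concern.** Adherence to a measurement method standardises technique. It does not hide treatment status from the person placing the margins on the film. Here the information that could influence a reading (whether and when the knee was re-injected) is the same variable that defines the compared subgroups. A tendency common to all knees would cancel between subgroups, but one linked to re-injection would not.

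JSN is the only structural efficacy parameter. WOMAC, VAS and the patient's global rating come from patients who know their treatment, and the tablet counts come from their diaries. Film reading is the one read-out that can still be masked after an open visit, so the plan's claim of objectivity matters most here. At stake is whether a nominally significant JSN difference reflects the joint or the reading.

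**Working it through.** The plan states no standard deviation, reading error, effect size or calculated sample size for JSW or JSN, so there is no figure of its own to reproduce. The check asks how often the planned test would reject if there were no true structural difference but the re-injected knees were read with a systematic shift.

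**Inputs from the documents**
- Maximum of 72 patients (SAP 3.3).
- Three subgroups, analysis of variance, two-sided 5% (SAP 3.1.3 and 3.4).

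**Assumptions, not in the documents**
- JSN is analysed as a quantitative variable.
- All 72 patients contribute.
- Both re-injected subgroups are shifted by the same amount b, in SDs of the analysed JSN variable.
- Subgroup sizes are, in the order not re-injected / re-injected from Visit 1 / re-injected from Visit 3: 24/24/24, 30/27/15 or 15/30/27.

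**Formula.** With n0 patients not re-injected and n1 re-injected in total, the non-centrality parameter is λ = b² × n0 × n1 / 72. The rejection rate is P(F′ > 3.13), where F′ is non-central F with 2 and 69 degrees of freedom and 3.13 is the 5% critical value.

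Multipliers n0 × n1 / 72:
- 24/24/24: 24 × 48 / 72 = 16
- 30/27/15: 30 × 42 / 72 = 17.5
- 15/30/27: 15 × 57 / 72 = 11.875

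Worked case, 24/24/24 at b = 0.5: λ = 0.25 × 16 = 4.0, which gives a rejection rate of 40.0%.

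| Shift b (SD) | 24/24/24 | 30/27/15 | 15/30/27 |
|---|---|---|---|
| 0 | 5.0% | 5.0% | 5.0% |
| 0.1 | 6.2% | 6.3% | 5.9% |
| 0.2 | 9.9% | 10.4% | 8.6% |
| 0.3 | 16.7% | 17.9% | 13.5% |
| 0.5 | 40.0% | 43.3% | 30.6% |

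Other splits of 72 give similar results at 0.5 SD: 34.4% for 18/36/18 and 44.3% for 36/24/12. With 60 patients (20/20/20) the rate is 33.7%.

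**Which readings are exposed.** If the comparison uses a value recorded at Visit 0 of the 2019 study, that reading predates any injection and only the Visit 5 reading is open to bias. If the 2019 films are re-read now, both readings are. The calculation applies either way, because b is the net shift.

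**The case against.** **The documents do not say that films are read unmasked.** The blinding statement concerns the study as a whole, and Visit 5 does not say who measures the film or where. The supplied protocol text is a synopsis and the SAP refers to other protocol sections, so a reading manual may exist elsewhere. This stands as a limit: the plan permits unmasked reading but does not prescribe it. Even so, the SAP section that relies on the safeguard should state it or cite it.

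**A reader might infer that the 2019 baseline is read retrospectively, or that the treating centre measures the films.** The documents support neither. In item 9 of SAP 3.1.3 the word retrospectively most naturally describes the comparison, and no measuring site is named.

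**The magnitude rests on assumed shifts.** This is correct. Nothing in the documents supports a particular b or its direction. All patients had the device, and Group A is re-injected after an inadequate pain response, so expectation could run either way. At 0.1 SD the inflation is slight, and the upper figures depend on the split. If JSN is a grade, the test is chi-square and these rates do not apply directly.

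**A 5% benchmark means little here.** Subgroups follow need for treatment, so a significant difference would not show a treatment effect even with masked reading. This also stands, and it limits what masking can achieve.

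**The consequence is limited.** The main purpose is safety, JSN is the last of nine efficacy parameters, and the stated tasks do not include structure. That bears on priority. It does not answer the point.

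**Conclusion.** The point holds as a permitted and avoidable bias. SAP 1.1.2 presents JSW as protected from subjectivity on the sole condition of following a methodology, while the supplied documents contain no masking of the reader to an openly given re-injection that defines the tested subgroups. At least the Visit 5 reading is exposed.

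The rates (about 6% at 0.1 SD, 9-10% at 0.2 SD, 13-18% at 0.3 SD and 31-43% at 0.5 SD, against 5%) illustrate sensitivity under the stated assumptions. They do not estimate the bias in this trial. A reader might conclude that the JSN results will be biased, or that masking would make the subgroup contrast causal. The documents support neither. The contrast stays confounded by need for treatment. With no radiograph listed at open-study Visit 0, the change also spans the 2019 treatment course.

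This is a cheap improvement worth making. It is not a defect that threatens the safety objective.

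**What to change.** - In SAP 1.1.2 and Protocol Visit 5, state that the JSW and JSN values used in the analysis are measured by the existing readers from coded copies of the 2019 Visit 0 film and the open-study Visit 5 film. Readers are masked to subgroup, injection history, clinical scores and film order. Masking the order also protects the all-patient change from baseline.
- Where a reader would know the patient, exchange coded films among the four centres. No additional reader is needed.
- State how JSN is derived from JSW and whether it is analysed as a measurement or a grade, since this decides between analysis of variance and chi-square.
- Report the JSN subgroup comparison as descriptive, because masked reading does not remove confounding by need for treatment.
- If masked reading is not adopted, remove the claim that JSW is objective. This corrects the wording only and changes no measurement.

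**Cost.** Wording changes in two documents, and coding and transfer of at most 72 × 2 = 144 films. The readings used for analysis become available later than the visit. No visit, radiograph or treatment rule changes.
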